LINEBERGER COMPREHENSIVE CANCER CENTER
CLINICAL ONCOLOGY RESEARCH PROGRAM
UNIVERSITY OF NORTH CAROLINA AT CHAPEL HILL

RESEARCH PROTOCOL

STUDY NUMBER(S): LCCC1612

PROTOCOL(S) TITLE: P53 mutational status and circulating free HPV DNA for the management of HPV-associated Oropharyngeal Squamous Cell Cancers

SPONSOR: Lineberger Comprehensive Cancer Center

AMENDMENT NUMBER: Amendment 15

VERSION DATE: 18August2023

Protocol Amendment #15

LCCC 1612: P53 mutational status and circulating free HPV DNA for the management of HPV-associated Oropharyngeal Squamous Cell Cancers

AMENDMENT INCORPORATES:

- Editorial, administrative changes
- Scientific changes
- Therapy changes
- Eligibility Changes

Rationale for amendment: The purpose of this amendment is to remove patient reported assessments and updated protocol reporting requirements.

Editorial, administrative changes:

Throughout Grammatical and mechanical edits made throughout

Throughout Protocol PI updated to [name], additional co-investigators and study personnel removed from protocol.

Scientific changes:

Section 2.2.3 Secondary objective and endpoint comparing head and neck quality of life before, during and after CRT removed.

3.2.3

Section 2.2.4 Secondary objective and endpoint comparing speech and swallowing function before and after CRT removed.

324

Section 5.11 All patient assessments removed, including Quality of Life and Patient Reported Outcomes as well as Speech and Swallow evaluations

Section 5.12 Languaged related to QOLs, PROs and the EAT-10 assessment relative to study duration removed.

Section 6.2 Language relative to reporting updated to add justification lack of trial related adverse event reporting. Language for affiliate sites and UNC removed

Section 7.2 References to QOLs, PROs, and speech and swallow function removed from statistical analysis section.

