1.2 Standard of care CRT for OPSCC

The standard treatment regimen for HPV-associated oropharyngeal or unknown primary squamous cell carcinoma of the head and neck is 70 Gy, 2 Gy per day, 35 fractions, over 7 weeks with 2 to 3 doses of cisplatin 100mg/m². Most institutions perform a PET/CT at 10 to 16 weeks after CRT to assess response. Depending on the clinical response, patients may have to have a biopsy of the primary site and/or a neck dissection after treatment. Typically patients with a negative PET/CT scan are observed (i.e. no surgery). Standard CRT is associated with significant acute toxicity with most patients experiencing grade 3 and 4 acute toxicity during treatment. Furthermore, approximately 20% of patients will have Grade 3-4 long-term morbidity related to their definitive CRT.

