1.3 HPV related OPSCC

The incidence of OPSCC is increasing and is thought to be secondary to HPV infection of the oropharyngeal mucosa¹⁻⁸. Evidence is accumulating that suggests that HPV-

positive HNSCC may be a distinct clinical and biological entity. The affected individuals are more likely to be white men, younger than 60 years of age, unmarried, and have a minimal history of alcohol or tobacco use^{3,9-30}. HPV-positive HNSCC has a higher response rate to neoadjuvant chemotherapy and in general has a better prognosis to therapy as compared to HPV-negative HNSCC^{10,13,18,19,22}. Biologically, the HPV oncoproteins E6 and E7 inactivate the tumor suppressor proteins p53 and pRb, respectively. Inactivation of pRb by E7 leads to upregulation of the p16 tumor suppressor protein. Thus, overexpression of p16 may be regarded as a biomarker for HPV-positive HNSCC^{18,29}. Furthermore, HPV-positive HNSCC is more likely to be associated with a wild-type p53, unlike tobacco-induced HNSCC¹¹. Because of the observed improved prognosis and distinct molecular profile, some have suggested that HPV-positive tumors may be more sensitive to CRT. The standard CRT regimen for most HNSCC is 70 Gy with 3 cycles of concurrent cisplatin at 100mg/m²³¹. Less intensive chemotherapy and/or radiation may be just as effective in HPV-related oropharyngeal HNSCC and reduce the severity of acute toxicity and long-term morbidity associated with CRT.

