2.2 Secondary Objectives

To prospectively assess if the changes in plasma circulating free HPV DNA during and after treatment are associated with clinical outcomes in patients with HPV-associated OPSCC. Hypothesis: Changes in levels of plasma circulating free HPV DNA during and after treatment will correlate with cancer control rates.

To assess the 2 year clinical outcomes of local control (LC), regional control (RC), local-regional control (LRC), distant metastasis free survival (DMFS), and overall survival (OS).

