3.0 ENDPOINTS

3.1 Primary Endpoint

Patients with HPV-positive and/or p16-positive OPSCC will receive de-intensified CRT. The 2 year PFS will be evaluated. Our null hypothesis (H_0) is that the PFS rate is 93% and our alternate hypothesis (H_1) is that the PFS rate is 86%.

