6.0 ADVERSE EVENTS

6.1 Definition

An adverse experience is any untoward medical occurrence in a patient or clinical investigation subject administered a pharmaceutical product and which does not necessarily have a causal relationship with this treatment. An adverse experience or event (AE) can therefore be any unfavorable and unintended sign (including an abnormal laboratory finding), symptom, or disease temporally associated with the use of a medicinal (investigational) product, whether or not related to the medicinal (investigational) product.

Hospitalization for elective surgery or routine clinical procedures that are not the result of an AE (e.g., surgical insertion of central line) need not be considered AEs and should not be recorded as an AE. Disease progression should not be recorded as an AE, unless it is attributable by the investigator to the study therapy.

In this study, toxicity will be assessed according to the NCI Common Terminology Criteria for Adverse Events (CTCAE), version 4.0, available at:
http://ctep.cancer.gov/protocolDevelopment/electronic_applications/ctc.htm.

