7.2 Data Analysis Plan

The main hypothesis test will be performed as described above. Subgroup analyses to compare PFS between patients with ≤ 10 pack years vs patients with > 10 pack years (but with no p53 mutation) smoking history will be conducted using log-rank test. Additionally, a Kaplan-Meier curve will be estimated for PFS, local control, regional control, local-regional control, distant metastasis free survival and overall survival. Circulating free HPV DNA before, during, and after CRT will be compared, using the paired t-test or McNemar's test as appropriate. As an exploratory analysis, joint modeling of longitudinal cfHPV-DNA and time-to-progression will be conducted to examine the association between time-varying cfHPV-DNA and disease progression. We will also perform exploratory analyses of the other genetic alterations that are assessed by the TruSight Tumor Panel® and fluorescent in-situ hybridization studies.

In addition to the above, other exploratory analyses utilizing study-related data may be performed. These analyses will be consistent with the overarching aims of the study.

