10.2 Time and Events Table

Study Assessments	Every 6 months for 2 yrs after CRT, then yearly	Every 2-3 Months for 2 yrs after CRT, every 6 months for 3 yrs then yearly ¹	3, 6, 12, 18 and 24 Months After CRT	10-16 Weeks After CRT	6-16 Weeks After CRT	Weeks 3 and 6 of CRT	Weekly During CRT	Prior to CRT
Clinical Evaluation				×				
Panendoscopy (if primary unknown) ²								
Contrasted neck CT (or PET/CT)								
Chest X-Ray				×				
Dental Evaluation ²								
Labs: CB, serum chemistries, liver function tests, pregnancy (F)								
HPV and/or p16 testing								
Genetic assessment (if > 10 pack year smoking history)								
Circulating free HPV-DNA (blood sample)	×	× ^{4,8}					×	
NCI-CTCAE (physician)	×		×		×			
Fiberoptic Laryngoscopy	×			×				
PET/CT					×			
Thyroid Function								× ⁷

Footnotes:

1. Exact timing of follow-up visits is flexible based on physician's standard of care
2. Strongly recommended, but not required
3. First post-CRT chest x-ray to be done 6 months after post-CRT PET/CT; Flexibility in timing is allowed based on scheduling of patient's appointments

4. Week 4 and 6 only
5. Additional post-treatment samples at PI's discretion
6. At provider's discretion
7. First one may be done at same time as first post-CRT chest x-ray; flexibility in timing is allowed based on scheduling of patient's appointments
8. See [Section 5.5](#) for details on time points based on enrollment date.

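### Physician CTCAE grading is specified but no endpoint or analysis summarises it, so the trial can accept the regimen on PFS with no planned estimate of harm.

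*Combined protocol and SAP*

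**What the plan says.** **Rationale.** Section 1.3 proposes that less intensive treatment may control HPV-related disease equally well and "reduce the severity of acute toxicity and long-term morbidity associated with CRT". Section 1.2 describes the burden of standard CRT: most patients have grade 3-4 acute toxicity, and "approximately 20% of patients will have Grade 3-4 long-term morbidity related to their definitive CRT".

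**Measurement.** Section 6.1 states: "In this study, toxicity will be assessed according to the NCI Common Terminology Criteria for Adverse Events (CTCAE), version 4.0". The Time and Events Table (10.2) has a physician CTCAE row with three marks.

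**Endpoints and analysis.** For the primary endpoint, section 3.1 says "The 2 year PFS will be evaluated". The clinical secondary objective in 2.2 is "To assess the 2 year clinical outcomes of local control (LC), regional control (RC), local-regional control (LRC), distant metastasis free survival (DMFS), and overall survival"; the other is cfHPV-DNA. Section 3.2 repeats these two groups. Section 7.2 adds the primary test, a log-rank comparison by smoking history, cfHPV-DNA and genetic analyses, and "Additionally, a Kaplan-Meier curve will be estimated for PFS, local control, regional control, local-regional control, distant metastasis free survival and overall survival". It also allows unspecified further exploratory analyses. None of these sections names a toxicity or function outcome.

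**Decision rule.** Under 7.1, failing to reject a 2-year PFS of 0.93 leads to the conclusion that the de-escalated treatment is no worse than standard RT.

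**Safety text.** Section 6.2 argues that toxicities can only be lower than historical norms, and concludes that adverse events will not be reported. Section 7.3 provides for monitoring by the principal investigator and summaries to the DSMC.

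**The concern.** De-intensification is worthwhile if cancer control holds and harm falls. The plan tests the first and assumes the second. It specifies an instrument for measuring harm but produces no number from it. A result accepted on PFS would therefore carry no planned toxicity rate for readers to weigh. An unexpectedly high acute rate in any regimen group would appear in no planned analysis.

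**Working it through.** **1. Reproduce the decision rule.** Inputs from 7.1: target accrual 250, dropout 10%, so 250 × 0.9 = 225 completers; reject H0 at 23 or more failures.

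- P(X ≥ 23 | n = 225, failure rate 0.07) = 0.0446. The plan states 0.045.
- P(X ≥ 23 | n = 225, failure rate 0.14) = 0.963. The plan states 0.96.

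The current design reproduces.

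**2. What the rule depends on.** Acceptance means 22 or fewer failures (22/225 = 9.8%).

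| True 2-year PFS | P(accept) |
|---|---|
| 0.93 | 0.955 |
| 0.90 | 0.51 |
| 0.86 | 0.037 |

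No toxicity term enters, so each value is the same at any toxicity rate.

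**3. What grading is scheduled.** The table's columns are scrambled in the text available. Two rows show how to read it. If the cells run in the reverse of the header order, PET/CT falls at 10-16 weeks after CRT, as in 5.8, and thyroid testing falls every 6 months, as in 5.12. Read in header order, thyroid testing would fall before CRT, which 5.12 contradicts. On the reversed reading the three CTCAE marks are before CRT, weeks 3 and 6 of CRT, and 10-16 weeks after CRT. Some rows have lost marks, so this is an inference to check against the intact table. It shows acute grading and no later time point.

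**4. Does 6.2 make measurement unnecessary?** Its argument describes patients receiving 60 Gy with either no chemotherapy or weekly cisplatin 30 mg/m². Sections 5.1 and 5.6 give p53-mutated patients with more than 10 pack years 70 Gy, with one further chemotherapy dose. Section 5.7 allows cisplatin 30 to 40 mg/m² and three other regimens. So the description does not cover everyone treated. Section 6.2 also presents RTOG 0129 as using the same de-intensified treatment, while 1.4 describes it as accelerated versus standard fractionation with cisplatin. These passages must be reconciled.

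**5. Precision available.** Exact (Clopper-Pearson) 95% CIs, assuming all 250 are treated and assessed. The rates are assumptions, since the documents give no target.

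| Patients with grade ≥3 | Rate | 95% CI |
|---|---|---|
| 50/250 | 20% | 15.2% to 25.5% |
| 125/250 | 50% | 43.6% to 56.4% |
| 200/250 | 80% | 74.5% to 84.8% |

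The size of the 70 Gy group is not given. With no events in n patients the exact upper limit is 1 − 0.025^(1/n). If n = 10 this is 1 − 0.692 = 30.8%; if n = 20 it is 1 − 0.832 = 16.8%. That group may support only a loose estimate.

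**The case against.** **The trial asks a different question.** The primary objective (2.1) is whether p53 status can select smokers for de-intensification, judged by PFS, and 1.5 says the two earlier studies showed a favourable toxicity profile. This stands in part. A reader might infer that the trial fails its own objective by omitting toxicity; it does not, because reduced toxicity is the background rationale and not a stated objective. But LCCC 1120 took patients with 10 or fewer pack years, and LCCC 1413 extended this only to 30 pack years with at least 5 years' abstinence (1.5). The present trial removes that limit, so the earlier data do not fully cover its new patients.

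**Toxicity is handled elsewhere.** The exploratory clause in 7.2 is optional and names no measure, window or population. DSMC review under 7.3 is oversight, not an estimate.

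**Late data may not exist.** This stands. It is tempting to say that 225 patients could distinguish a halved late-morbidity rate from the 20% in 1.2. The interval arithmetic works (22/225 gives 6.2% to 14.4%), but no late CTCAE time point is shown to be scheduled, and the summary for Amendment 8 records adverse event reporting limited to 30 days after treatment. The 20% is approximate and historical. Section 6.2 cites about 25% in wording that could mean either a rate or a fraction of the control rate. Also, 225 is the expected number of PFS completers, whereas toxicity belongs to all treated patients.

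**Quality of life and swallowing.** The summary for Amendment 15 records "References to QOLs, PROs, and speech and swallow function removed from statistical analysis section". A reader might infer that a body of collected data will be wasted. The documents show neither how much was collected nor the removed analysis text, and exploratory use remains allowed.

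**Conclusion.** The point holds in a limited form. CTCAE grading is specified, lower toxicity is the stated rationale, and no objective, endpoint or analysis summarises toxicity. The acceptance probability (0.955 at a true PFS of 0.93) is independent of harm, and the number of planned toxicity estimates is zero.

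This does not invalidate the PFS test, whose current figures reproduce. It limits what the trial can say about the value of de-intensification. The conclusion rests on the current text of 2.2, 3.2, 6.1, 6.2, 7.2 and 10.2; the timing of the grading rests on the reading of the table above. It does not extend to a claim that the existing data could demonstrate lower late morbidity. With one arm and no concurrent comparator, any toxicity result would be descriptive.

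**What to change.** 1. Add to 3.2 and 7.2 a descriptive secondary endpoint: the proportion of all treated patients with any CTCAE v4.0 grade 3 or higher event from the start of CRT through the 10-16 week post-CRT assessment, with an exact 95% CI. Report it overall and by regimen received (60 Gy without chemotherapy, 60 Gy with chemotherapy, 70 Gy), with the number assessed at each time point.
2. Reconcile the statement in 6.2 that adverse events will not be reported with the grading in 6.1 and 10.2, and its account of RTOG 0129 with 1.4.
3. Report later toxicity, and any quality-of-life or swallowing data gathered before August 2023, only descriptively and only where already collected, with completeness stated.

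The cost is analysis-plan wording, a conforming edit to 6.2 and a few tables. It needs no added patients and no visits beyond those that 10.2 appears to schedule. The downsides are uneven completeness and a possibly small 70 Gy group. Regimen groups also differ by stage, smoking and p53 status, so differences between them should not be read as treatment effects.

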7.3 Safety Meetings

The principal investigator will provide continuous monitoring of patient safety in this study with periodic reporting to the Data Safety Monitoring Committee (DSMC).

The principal investigator will submit summaries, together with formatted reports, to the DSMC for review. The reports will be reviewed at the time of the appointed meeting schedule established by this committee. Following review, the DSMC will report its recommendations, together with the principal investigator report, to the Oncology PRC. These reports will be reviewed by the PRC at the time of the study's annual IRB renewal. When warranted, the PRC and/or DSMC will have the prerogative to request additional information.

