7.0 STATISTICAL CONSIDERATIONS

7.1 Study Design/Study Endpoints

The main objective of this Phase-II trial is to estimate the two-year progression-free survival probability (PFSP) in this group of patients treated with de-escalated radiotherapy. The planned total sample size is 80 patients. (This number was increased to 120 as of July 7, 2017, 140 as of February 7, 2019, 160 as of May 29, 2019, 180 as of October 9, 2019, 200 as of January 7, 2020, and 250 as of June 17, 2020. Please see details below.) The recruitment phase is expected to last 48 monthsDrop out is expected to be about 10%, based on a previous trial (LCCC 1120), hence we expect a total of 225 patients to complete the study.

The statistical aim is phrased as a hypothesis test with the null hypothesis being that the two-year PFSP is 0.93 and the alternative hypothesis being that the two-year PFSP is 0.86 (or less). A one sample binomial test will be used to assess this hypothesis. If the null hypothesis is rejected the conclusion will be that the de-escalated treatment is inferior to the standard treatment. If the null hypothesis is not rejected the conclusion will be that the de-escalated treatment is at least as good as the standard RT.

We give power calculations for two sample sizes. For a sample size of n=73 (patients who complete the study), the null hypothesis will be rejected if 11 or more patients fail. Failure is defined as not reaching the two-year time point progression-free. Defining P(Reject H0) to be the probability of rejecting the null hypothesis, the performance of the test is summarized in the following table.

True 2-year PFSP	P(Reject H0)
0.93	0.03
0.86	0.58
0.80	0.94
0.75	0.99

For a sample size of n=80 patients, the null hypothesis will be rejected if 12 or more patients fail. The performance of the test is summarized in the following table.

True 2-year PFSP	P(Reject H0)
0.93	0.02
0.86	0.57
0.80	0.94
0.75	0.99

For n=73 to 78, the critical point is 11 failures. For n=79 and 80, the critical point is 12 failures. With these critical points, type-I error ranges from 0.023 to 0.045 depending on sample size.

Sample size and power re-calculation: On July 7, 2017, the PI, noticing the higher than expected patient accrual rate, decided to increase sample size to 120. This should result in

about 108 patients to complete the study, after accounting for drop-out with an expected drop-out rate of 10%.

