0.75	1.00

For n=159 to 161, the critical point is also 18 failures. With these critical points, type-I error ranges from 0.030 to 0.035 depending on sample size.

Sample size and power re-calculation: On January 7, 2020, the PI, waiting for the opening of LCCC 1912 and noticing the completion of accruing planned 180 patients, decided to increase sample size to 200. This should result in about 180 patients to complete the study, after accounting for drop-out with an expected drop-out rate of 10%.

For a sample size of n=180 patients, the null hypothesis will be rejected if 19 or more patients fail. The performance of the test is summarized in the following table.

True 2-year PFSP	P(Reject H0)
0.93	0.048
0.86	0.93
0.80	0.99
0.75	1.00

For n=177 to 179, the critical point is also 19 failures. With these critical points, type-I error ranges from 0.042 to 0.048 depending on sample size.

Sample size and power re-calculation: On June 17, 2020, the PI, waiting for the opening of LCCC 1912 and noticing the completion of accruing planned 200 patients, decided to increase sample size to 250. This should result in about 225 patients to complete the study, after accounting for drop-out with an expected drop-out rate of 10%.

For a sample size of n=225 patients, the null hypothesis will be rejected if 23 or more patients fail. The performance of the test is summarized in the following table.

True 2-year PFSP	P(Reject H0)
0.93	0.045
0.86	0.96
0.80	0.99
0.75	1.00

For n=220 to 224, the critical point is also 23 failures. With these critical points, type-I error ranges from 0.036 to 0.045 depending on sample size.

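### Reaching the plan's own critical failure count triggers neither a pause in any open enrolment nor an unscheduled DSMC review

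*Combined protocol and SAP*

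**What the plan says.** Section 7.1 sets one test: "The statistical aim is phrased as a hypothesis test with the null hypothesis being that the two-year PFSP is 0.93", with "the alternative hypothesis being that the two-year PFSP is 0.86 (or less") and "A one sample binomial test will be used to assess this hypothesis". The event is defined by "Failure is defined as not reaching the two-year time point progression-free". For the current target of 250 enrolled, "For a sample size of n=225 patients, the null hypothesis will be rejected if 23 or more patients fail"; the same count is given for 220 to 224 completers. The consequence is explicit: "If the null hypothesis is rejected the conclusion will be that the de-escalated treatment is inferior to the standard treatment".

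Section 7.2 carries out this main test and describes no interim look. Oversight is in section 7.3: "The principal investigator will provide continuous monitoring of patient safety in this study with periodic reporting to the Data Safety Monitoring Committee (DSMC"). The DSMC reviews the reports on its own meeting schedule and sends recommendations to the PRC, and "These reports will be reviewed by the PRC at the time of the study's annual IRB renewal". Either body may ask for more information. No section states a failure count, a PFS threshold, a pause or an unscheduled meeting.

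Section 7.1 also records six increases in the target, from 80 to 250. The reasons given are fast accrual for the first two and the wait for LCCC 1912 to open for the other four. None mentions the failures seen so far.

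**The concern.** The main risk in a de-escalation trial is excess cancer failure, and here that is also the primary endpoint. The sponsor has already fixed the number of failures that means the regimen is inferior. A patient who has progressed within two years stays a failure, so the count cannot fall. Once it reaches the critical number for the largest possible evaluable group, the conclusion is certain, yet nothing in the plan then has to happen.

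The route by which progressions reach the DSMC is also unstated. Section 6.1 keeps disease progression out of adverse event recording unless it is attributed to study therapy. Section 6.2 says adverse events will not be reported. Section 7.3 does not say that the reports contain progressions.

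At stake is how soon the DSMC and IRB learn of a settled unfavourable result and, if enrolment is open, how many more patients enter after that point.

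**Working it through.** **Inputs from the documents.** Null failure probability 1 − 0.93 = 0.07; alternative 1 − 0.86 = 0.14; critical number 23 at n = 225; target 250 with 10% dropout; recruitment 48 months; two-year endpoint (sections 7.1 and 5.11).

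**Step 1: reproduce the plan's figures.** With X binomial (225, p):
- P(X ≥ 23 | p = 0.07) = 0.0446 (plan: 0.045).
- P(X ≥ 23 | p = 0.14) = 0.9628 (plan: 0.96).
- At n = 220, P(X ≥ 23 | p = 0.07) = 0.0360 (plan: 0.036).

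The current rule reproduces.

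**Step 2: critical number at other sizes.** I take the smallest r with P(X ≥ r | n, 0.07) ≤ 0.05. The 0.05 ceiling is an assumption: section 7.1 does not name a level, but its stated type I error ranges never exceed 0.050.

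| Evaluable n | Critical number | Check |
|---|---|---|
| 216 to 227 | 23 | 0.0484 at 227; 0.0505 at 228 |
| 228 to 239 | 24 | 0.0486 at 239 |
| 240 to 250 | 25 | 0.0468 at 250; 24 failures would give 0.0733 |

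So 23 failures settle the result if no more than 225 patients can be evaluable. 25 settle it for any number up to 250, because smaller groups need fewer failures.

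**Step 3: effect of a pause.** The pause acts only when the final test is bound to reject, whether enrolment then resumes or ends. It moves no trial from one conclusion to the other. At 225 completers, type I error stays 0.0446 and power 0.9628.

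**Step 4: how early the count is reached.** I simulated 20,000 trials per row with 250 patients and a threshold of 25. Assumptions not in the documents: uniform accrual, constant hazard, no dropout, failures known when they occur, and the two-year clock starting at entry. Main figures use 48 months of accrual; brackets give 36 to 60 months. Final readout is 24 months after the last enrolment.

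| True 2-year PFS | Count reached before last enrolment | Mean enrolled afterwards, capped at 50 | Median months from count to final readout |
|---|---|---|---|
| 0.93 | 0.2% (0.02% to 0.4%) | – | – |
| 0.86 | 64% (40% to 76%) | 28 (22 to 33) | 27 (23 to 30) |
| 0.80 | 99% (96% to 99.7%) | 47 (40 to 48) | 37 (30 to 43) |

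The third column covers trials in which the count comes before the last enrolment; repeat runs at PFS 0.86 gave 28 to 29. The last column covers all trials that reach the count. At PFS 0.93 the count is reached at any time in 4.7% of trials.

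The cap is 250 − 200 = 50. The target became 250 on 17 June 2020, when section 7.1 records that 200 had been accrued, so no more than 50 patients could be enrolled under the current threshold.

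**The case against.** **Oversight exists.** The principal investigator monitors continuously, the DSMC meets on its own schedule and can make recommendations, and section 8.5.1 allows immediate action against a hazard. This stands. A reader might infer that nothing can happen until the annual PRC review; section 7.3 does not say that a DSMC recommendation is suspended until then. What is missing is a numerical trigger and a required action.

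**Large numbers enrolled after a settled result.** Without the cap, the same simulation gives means of about 65 patients at PFS 0.80 and 91 at 0.75. The recent pace (60 patients from 29 May 2019 to 17 June 2020, 60/12.6 ≈ 4.8 a month) gives about 57 in a year. The documents do not support these figures under the current target, because only 50 places remained. In the simulation the 25th failure often precedes the 200th enrolment (74% of trials at 0.80), when a smaller target with its own lower critical number was in force.

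**Enrolment may be closed.** At that pace the last 50 patients take 50/4.8 ≈ 10.5 months, to about May 2021, well before the version of 18 August 2023. Two years of follow-up would then end around mid-2023. This is inference, since the documents give neither enrolment status nor failure counts, but it is plausible. The months in the table describe a rule in force throughout; what could still be gained at the version date may be much less.

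**The plan has not already rejected the regimen.** A reader might infer that it has. Reaching the count makes rejection certain, but the test itself comes at the end, and the certainty holds only while the maximum size stays fixed. Six increases show that it may not: the number was 16 at n = 144, 19 at n = 180 and 23 at n = 225.

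**Whose failures?** Section 5.6 plans patients with more than 10 pack-years and a p53 mutation to 70 Gy, and section 7.1 does not say whether they are in the tested group. A trigger that leaves this open could be met partly by failures outside the de-intensified regimen. This objection stands and shapes the fix.

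**Conclusion.** The point holds as a design gap, not as a contradiction in the plan or evidence of what happened in the trial. The plan defines a count that settles an unfavourable conclusion and attaches no action to it.

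Its size depends on a fact the documents omit:
- **Enrolment closed:** the benefit is earlier DSMC review and reporting, by a median of up to about 27 months at true PFS 0.86 had the rule applied throughout.
- **Enrolment open:** at most 50 patients are affected. Where the count comes first, about 28 to 29 are enrolled afterwards at PFS 0.86 and about 47 at 0.80.

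The critical numbers are exact, given the 0.05 ceiling. The timing figures rest on uniform accrual, constant hazard and immediate knowledge of failures; delay in confirming failures would reduce them. The change is worth making because it costs little and affects no error rate.

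**What to change.** Add to sections 7.1 and 7.3:

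1. Confirmed failures are counted continuously and reported to the DSMC, using the same failure definition and population as the primary binomial test. State whether p53-mutated patients planned to 70 Gy are in that population.
2. When the count reaches the critical number for the maximum evaluable size (25 for up to 250; 23 once no more than 225 can be evaluable), any open enrolment pauses and the DSMC meets outside its schedule.
3. The DSMC's recommendation goes to the principal investigator and the IRB without waiting for the annual PRC review.
4. Any further increase in the target requires that the DSMC first see the current failure count.

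The protocol should also state whether enrolment is open. The change concerns enrolment and review only, not the treatment of patients already enrolled.

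The cost is a paragraph of text and a running tally of primary-endpoint events. No alpha is spent and no patients are added. The downside is a possible unscheduled meeting (the count of 25 is reached at some time in about 4.7% of trials at true PFS 0.93 with 250 evaluable) and, in about 0.2% of such trials, a pause in enrolment.
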